**After administration of study drug, the following post treatment procedures and assessments will be performed:**

- Vital sign measurements (sitting blood pressure, heart rate, respiratory rate, oral temperature): 30 minutes, 1 hour, and 2 hours following completion of the infusion; abnormal results to be repeated after 5 minutes of rest ([Section 6.5](#))
- Pulse oximetry: 30 minutes, 1 hour, and 2 hours following completion of the infusion ([Section 6.5](#))
- PK sample collection at 5 minutes, 1 and 2 hours after the completion of study drug infusion; record collection date and time for each PK sample ([Section 6.7](#))
- 12 Lead ECG (to be obtained in triplicate at 5 minutes after the completion of study drug infusion ([Section 6.6](#)))
- Concomitant medication assessment ([Section 6.10](#))
- AE assessment ([Section 6.9](#))

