**After administration of study drug, the following post treatment procedures and assessments will be performed:**

- Vital sign measurements (sitting blood pressure, heart rate, respiratory rate, oral temperature): 30 minutes, 1 hour, and 2 hours following completion of the infusion; abnormal results to be repeated after 5 minutes of rest ([Section 6.5](#))
- Pulse oximetry: 30 minutes, 1 hour, and 2 hours following completion of the infusion ([Section 6.5](#))
- Day 28 ONLY: PK sample collection at 5 minutes, 1 and 2 hours after the completion of study drug infusion; record collection date and time for each PK sample ([Section 6.7](#))
- Day 28 ONLY: 12 Lead ECG (to be obtained in triplicate at 5 minutes after the completion of study drug infusion) ([Section 6.6](#))
- Concomitant medication assessment ([Section 6.10](#))
- AE assessment ([Section 6.9](#))

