**APPENDIX 3. COHORT 2 ALTERNATIVE WEEKLY MAINTENANCE SCHEDULE OF EVENTS TABLE**

**Table 10. Study Assessments for Cohort 2; Alternative Weekly Maintenance Schedule**

Visit Number	Screening	Loading			Maintenance										Follow-Up		
	1	2	3	4	5	6	7	8	9	10	11	12	13	14	15	16	17
Time Point (Study Day)	-28 to -1	0 Baseline	7 (±1 d)	14 (±1 d)	21 (±3 d)	28 (±3 d)	35 (±3 d)	42 (±3 d)	49 (±3 d)	56 (±3 d)	63 (±3 d)	70 (±3 d)	77 (±3 d)	84 (±3 d)	91 (±5 d) or ET Visit	112 (±5 d)	140 (±5 d) EOS Visitg
Informed consent	X																
Demographics/medical history	X																
Inclusion/exclusion	X																
Physical examination a	X	X	X	X	X	X	X	X	X	X	X	X	X	X	X		X
Vital signs b	X	X	X	X	X	X	X	X	X	X	X	X	X	X	X	X	X
Karnofsky Performance Scale	X																
Pulse oximetry c		X	X	X	X	X	X	X	X	X	X	X	X	X			
Clinical safety labs d	X	X	X	X	X	X	X	X	X	X	X	X	X	X	X		X
Pregnancy test e	X	X			X										X		X
Hepatitis and HIV antibody screen	X																
12-lead ECG f	X	X		X	X										X		X
Tetanus and VZV antibodies g		X			X										X		X
Cold agglutinins (titer and thermal amplitude)		X			X										X		X
PK sampling h		X	X	X	X									X			
Immunogenicity i	X	X	X	X	X	X	X	X	X	X	X	X	X	X	X	X	X
Study drug administration j		X	X	X	X	X	X	X	X	X	X	X	X	X			
Immunoglobulins k	X	X	X	X	X	X	X	X	X	X	X	X	X	X	X l	X l	X l
CIC		X	X	X	X	X	X	X	X	X	X	X	X	X	X	X	X
Haptoglobin	X	X	X	X	X	X	X	X	X	X	X	X	X	X	X	X	X
Direct Coombs test	X	X		X	X										X		X
Additional PD sample collections m		X			X										X		
FCGR2A by buccal swab n		X															
RNA sequencing		X			X										X		
Immunophenotyping o		X			X										X		

Quantitative Coombs assay		X		X	X			X						X		
Adverse events	To be collected from the date that the ICF is signed through the last study visit															
Concomitant medications	To be collected from within at least 3 months prior to screening through the last study visit															

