2.1.2 Secondary Objectives and Endpoints

Secondary Objectives	Secondary Endpoints
To evaluate the efficacy of doses of SYNT001 at different dose levels and dosing regimens on PD biomarkers	The evaluation of PD biomarkers based on absolute serum levels and percent change from baseline of total IgG, IgG subtypes (IgG1-4), immunoglobulin A (IgA), immunoglobulin M (IgM), albumin, and CIC summarized by dose, dosing regimen and time point
To determine the PK of SYNT001 following IV infusions at different dose levels and dosing regimens	The determination of PK parameters including half-life ($t_{1/2}$), maximum serum concentration determined directly from the concentration-time profile (C_{max}), observed time of peak serum concentration (T_{max}), area under the serum concentration-time curve from pre-dose ($time_0$) to 24 hours post-dose (AUC_{0-24}), and area under the serum concentration-time curve from pre-dose ($time_0$) to infinity ($AUC_{0-\infty}$), (Cohort

Secondary Objectives	Secondary Endpoints
	1); maximum serum concentration determined directly from the maximum serum concentration and corresponding T_{max} (Cohort 2) summarized by dose, dosing regimen and time point
To assess the efficacy of doses of SYNT001 at different dose levels and dosing regimens on disease markers	The assessment of WAIHA disease activity by absolute changes in the disease activity markers of hematocrit, hemoglobin, platelet count, reticulocyte count, lactate dehydrogenase (LDH), haptoglobin, and total and indirect bilirubin will be summarized by dose, dosing regimen and time point The direct Coombs test result (positive or negative) will be summarized by dose, dosing regimen and time point
To measure the immunogenicity of SYNT001 administered at different dose levels and dosing regimens	The immunogenicity of SYNT001, as determined by presence of anti-SYNT001 binding antibodies and neutralizing antibodies, summarized by dose, dosing regimen and time point

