3.2.11 Pharmacokinetics (PK) Sampling

The following PK parameters will be studied in Cohort 1: $t_{1/2}$, C_{max} , T_{max} , AUC_{0-24} , and $AUC_{0-\infty}$. For all successive cohorts, the PK parameters studied will be maximum serum concentration of SYNT001 and the associated T_{max} . Specific collection times are detailed in [Table 5](#).

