4.8 Analysis of Secondary Endpoints

4.8.1 Pharmacokinetic Analysis

PK results for SYNT001 will be summarized by cohort, visit and time point.

Descriptive statistics will be provided for the PK parameters including mean, SD, CV, median, minimum, and maximum.

For calculation of mean concentrations and generation of mean concentration-time profiles, all below the limit of quantification (BLQ) values will be set to zero except when an individual BLQ falls between 2 quantifiable values, in which case it will be omitted.

If there are values above the BLQ, but too sparse to allow full analysis, descriptive statistics will be performed on available values.

PK concentrations will be summarized descriptively at each nominal time point by cohort using n, mean, SD, percent coefficient of variation (CV%), standard error, median, minimum, maximum, geometric mean, geometric CV%.

Mean concentrations (\pm SD) of SYNT001 will be plotted on a linear and semi-logarithmic scale against nominal time points, by cohort. Individual concentration for each subject will be plotted using original scale and semi-log scale.

Study drug serum concentration data will be used to calculate the following PK parameters, if feasible:

Parameters	Description
C_{\max}	Maximum observed plasma concentration observed directly from data at Day 0 and Day 28
T_{\max}	Time to reach maximum observed concentration directly from data at Day 0 and Day 28
λ_z	Apparent first-order terminal elimination rate constant calculated by linear regression of the terminal linear portion of the log concentration vs. time curve at Day 0 and Day 28
$t_{1/2}$	Terminal elimination half-life, calculated as $\ln(2)/\lambda_z$ at Day 0 and Day 28
AUC_{0-24}	AUC from time zero to 24 hours post-dose administration at Day 0 and Day 28
AUC_{∞}	AUC from time zero to infinity time (as $AUC_{0-t} + C_{\text{last}}/\lambda_z$, where C_{last} is the last quantifiable concentration) at Day 0 and Day 28

Actual sampling time will be used for PK calculations. Actual sampling times that are outside the scheduled sampling times window described in [Table 5](#) will be excluded from summary statistics of average PK SYNT001 serum concentrations but will still be used in the calculation of PK parameters.

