- h. Serology: Testing at Day 56 will not be done for any subject whose baseline titer is below the level of detection. If the Day 56 results are greater than 30% below the baseline value, or if the subject falls below the level of detection, the subject will be re-tested at Day 84; if still below the baseline value (or level of detection), the subject will be re-tested at Day 112. Any subject whose baseline value for tetanus or VZV was above the detectable level at baseline and is not within 30% of the baseline value or is below the detectable level by Day 112, will be referred to their primary care physician for further management. See Protocol Section 6.7.3 for additional information.
- i. PK: Starting on Days 0 and 28, serum samples will be collected just prior to the start of study drug infusion (pre-dose), and at 5 minutes and 2, 4, 6, 24, and 48 hours after the end-of-study drug infusion. Additional samples will be collected on Days 5 and 33. See Protocol Section 6.7.4 for additional information.
- j. Immunogenicity: Blood samples will be collected pre-dose when collected on dosing days. Samples will be collected on Days 0, 14, 28, 56, 84 and 112. See Protocol Section 6.7.6 for additional information.
- k. Prior to study drug infusion, SYNT001 drug product is to be diluted in dextrose 5% in water to a total volume of 250 mL and administered intravenously over 1 hour ±15 minutes using a 0.2-micron, inline filter. See Protocol Section 9 for additional information.
- l. Immunoglobulins (IgG, IgA, IgM) and IgG subtypes (IgG1-4): Collected for measurements of IgG, IgG subtypes (IgG1-4), IgA, IgM at every visit. On Days 0, 7, 14, 21, and 28, samples are collected prior to infusion of study drug.
- m. Subjects will return to the clinic on Days 84 and 112 for follow-up visits. Subjects whose total IgG is not within 30% of their Day 0 baseline value and not above 500 mg/dL at the Day 112 visit will be referred for further management.
- n. Additional PD samples to be collected for measurements of biomarkers, including D-dimer; antiphospholipid antibodies (lupus anticoagulant, anti-cardiolipin, and anti-beta-2-GP1 antibodies); antinuclear antibody titer; anti-double-stranded DNA antibody titer; complement component 3. See Protocol Section 6.7.5 for complete information.
- o. Buccal samples to be collected and stored.
- p. Immunophenotyping by flow cytometry for measurement of CD3⁺CD4⁺ T, CD3⁺CD8⁺ T, monocytes, natural killer (NK) cells, and B cells.

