- j. Prior to study drug infusion, SYNT001 drug product is to be diluted in dextrose 5% in water to a total volume of 250 mL and administered intravenously over 1 hour ±15 minutes using a 0.2-micron, inline filter. See Protocol Section 9 for additional information.
- k. Immunoglobulins (IgG, IgA, IgM) and IgG subtypes (IgG 1-4): Collected for measurements of IgG, IgG subtypes (IgG1-4), IgA, and IgM at every visit. On dosing days, samples are collected prior to infusion of study drug. See Protocol Section 6.7.5 for additional information.
- l. Subjects will return to the clinic on Days 91, 112, and 140 for follow-up visits. Subjects whose total IgG is not within 30% of their Day 0 baseline value and not above 500 mg/dL at Day 140 will be referred for further management.
- m. Additional PD samples to be collected for measurements of biomarkers, including D-dimer; antiphospholipid antibodies (lupus anticoagulant, anti-cardiolipin, and anti-beta- 2-GP1 antibodies); antinuclear antibody titer; anti-double-stranded DNA antibody titer; complement component 3. Collect samples pre-dose on dosing days. See Protocol Section 6.7.5 for additional information.
- n. Buccal samples to be collected and stored.
- o. Immunophenotyping by flow cytometry for measurement of CD3⁺CD4⁺ T, CD3⁺CD8⁺ T, monocytes, natural killer (NK) cells, and B cells. Collect samples pre-dose on dosing days.

Table 4. Study Assessments for Cohort 2; Alternative Weekly Maintenance Schedule

Visit Number	Screening	Loading			Maintenance										Follow-Up		
	1	2	3	4	5	6	7	8	9	10	11	12	13	14	15	16	17
Time Point (Study Day)	-28 to -1	0 Baseline	7 (±1 d)	14 (±1 d)	21 (±3 d)	28 (±3 d)	35 (±3 d)	42 (±3 d)	49 (±3 d)	56 (±3 d)	63 (±3 d)	70 (±3 d)	77 (±3 d)	84 (±3 d)	91 (±5 d) or ET Visit	112 (±5 d)	140 (±5 d) EOS Visit^q
Informed consent	X																
Demographics/medical history	X																
Inclusion/exclusion	X																
Physical examination ^a	X	X	X	X	X	X	X	X	X	X	X	X	X	X	X		X
Vital signs ^b	X	X	X	X	X	X	X	X	X	X	X	X	X	X	X	X	X
Karnofsky Performance Scale	X																
Pulse oximetry ^c		X	X	X	X	X	X	X	X	X	X	X	X	X			
Clinical safety labs ^d	X	X	X	X	X	X	X	X	X	X	X	X	X	X	X		X
Pregnancy test ^e	X	X			X										X		X
Hepatitis and HIV antibody screen	X																
12-lead ECG ^f	X	X		X	X										X		X
Tetanus and VZV antibodies ^g		X			X										X		X
Cold agglutinins (titer and thermal amplitude)		X			X										X		X
PK sampling ^h		X	X	X	X									X			

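### SAP 4.8.1 derives Cmax and Tmax only at Day 0 and Day 28, which covers 2 of Cohort 2's 5 PK dosing days, or 1 of 5 on the weekly option

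*SAP*

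**What the plan says.** SAP 4.8.1 contains one table of PK parameters for the whole study. Its Cmax row reads "Maximum observed plasma concentration observed directly from data at Day 0 and Day 28". The rows for Tmax, the terminal rate constant, half-life and the two AUCs carry the same two days. No row names a cohort.

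SAP 3.2.11 gives Cohort 1 the full parameter set and then narrows it: "For all successive cohorts, the PK parameters studied will be maximum serum concentration of SYNT001 and the associated" Tmax. The secondary endpoint in SAP 2.1.2 asks for these two parameters to be reported as "Cohort 2) summarized by dose, dosing regimen and time point".

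Days 0 and 28 are where the Cohort 1 profiles begin. Footnote i to SAP Table 2 (Appendix A) reads "PK: Starting on Days 0 and 28, serum samples will be collected just prior to the start of study drug infusion (pre-dose" and so on, with later samples out to Days 5 and 33.

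Cohort 2 has a different schedule. On each PK day there is a pre-dose sample, and Protocol 7.2.2, 7.2.3 and 7.2.5 then call for "PK sample collection at 5 minutes, 1 and 2 hours after the completion of study drug infusion". For the maintenance visits before Day 84, Protocol 7.2.4 restricts this to one visit: "Day 28 ONLY: PK sample collection at 5 minutes, 1 and 2 hours after the completion of study drug infusion".

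**The concern.** The table appears to have been written for Cohort 1 and not adapted for Cohort 2. It lists AUC to 24 hours, for example, which Cohort 2 cannot support because its sampling stops 2 hours after the end of infusion.

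Cohort 2 is the part of the study in which dose level and regimen may vary, and its PK endpoint is meant to be reported by dose, regimen and time point. Loading and maintenance dose levels may differ. If Cmax and Tmax are not derived after the last loading dose or at the end of maintenance, the derived endpoint cannot describe peak exposure at those points. On the weekly option the table would yield no repeat-dose Cmax or Tmax for Cohort 2 at all, and it would ask for a Day 28 value for which no sample is scheduled.

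Protocol 11.4 sets no such day limit. SAP Section 1 says that substantial departures from the protocol will be identified, and none is identified here. That points to an oversight rather than a decision.

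**Working it through.** No sample size, power or alpha figure is involved, and the plan states no figure to reproduce. The check matches sampled days to derived days.

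**Inputs**

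- Derivation days: {0, 28} (SAP 4.8.1).
- Every-other-week schedule: the PK sampling row of SAP Table 3 and Protocol Table 3, 12 columns. Marks fall under Days 0, 7, 14, 28 and 84. There are 8 doses.
- Weekly option: the PK sampling rows of SAP "Table 4. Study Assessments for Cohort 2; Alternative Weekly Maintenance Schedule" and Protocol "Table 10. Study Assessments for Cohort 2; Alternative Weekly Maintenance Schedule", 17 columns. Marks fall under Days 0, 7, 14, 21 and 84. There are 13 doses. Day 28 is a dosing day with no PK mark.
- Cohort 2 size: up to 12 (SAP 3.1).
- Post-infusion samples per PK day in Cohort 2: 3 (5 minutes, 1 hour, 2 hours).

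**Cross-check of the days.** The every-other-week days agree with Protocol 7.2.2 (Day 0), 7.2.3 (Days 7 and 14), 7.2.4 (Day 28 only) and 7.2.5 (Day 84). Footnote h to Table 3 could be read as PK sampling at all 8 doses, but the grid and the Day 28 restriction in 7.2.4 fix the number at 5. Protocol 7.2 does not describe the weekly option, so its days rest on the two schedule tables alone.

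**Overlap with {0, 28}**

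| Schedule | PK days | Derived | Not derived | Share derived |
|---|---|---|---|---|
| Every other week | 0, 7, 14, 28, 84 | 0, 28 | 7, 14, 84 | 2/5 = 40% |
| Weekly option | 0, 7, 14, 21, 84 | 0 | 7, 14, 21, 84 | 1/5 = 20% |

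**Upper-limit counts, if 12 subjects complete with no missing samples**

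- Subject-occasions with PK: 12 × 5 = 60 on either schedule.
- Every other week: 12 × 2 = 24 derived and 12 × 3 = 36 not derived. Post-infusion samples feeding no derived parameter: 36 × 3 = 108.
- Weekly option: 12 × 1 = 12 derived and 12 × 4 = 48 not derived. Post-infusion samples feeding no derived parameter: 48 × 3 = 144.

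**Which doses are missed.** Day 14 is the third and last loading dose, and Day 84 is the final maintenance dose; neither is covered on either schedule. On the every-other-week schedule Day 28 is the first maintenance dose and is covered. On the weekly option maintenance starts on Day 21, so no maintenance dose is covered.

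**The case against.** The strongest reply is that the table is simply an unlabelled Cohort 1 table. Four of its six rows belong to or support the Cohort 1 parameter set, and the two days are Cohort 1's. On that reading Cohort 2 is governed by SAP 3.2.11, the endpoint wording in 2.1.2 and the opening of 4.8.1, which calls for summaries by cohort, visit and time point, and none of these limits the days. But the table's own wording does not confine it to Cohort 1. If it did, Cohort 2 would have no stated derivation days at all, and the same correction would be needed. The summary sentence says how results are shown, not which parameters are derived, and the condition that parameters be derived if feasible can only reduce the set.

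A second reply is that the first loading dose and first maintenance dose are a reasonable descriptive choice. That would be tenable on the every-other-week schedule if the SAP had stated it as a choice. It fails on the weekly option, where Day 28 is not sampled.

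Third, little may be lost. Concentrations on all five days are summarized at each nominal time, plotted and listed. If the peak falls close to the end of infusion, which is an assumption, the 5-minute summary would approximate Cmax. That stands as a limit on the impact. It does not supply the endpoint: a mean at one nominal time equals the mean of individual maxima only if every subject peaks then, and Tmax has no nominal-time equivalent.

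Finally, SAP Section 6 places derived-data specifications in separate documents, which may already add the days. They are not available here. If they do add them, they depart from the SAP text; if they follow it, the gap carries into the tables.

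**Conclusion.** The point holds. As written, SAP 4.8.1 derives Cohort 2's PK endpoint on 2 of 5 sampled dosing days, or 1 of 5 if the weekly option is adopted. These fractions rest on the schedule grids and do not depend on how many subjects enrol. The counts of 36 and 48 occasions without derived parameters are upper limits, because Cohort 2 may be smaller than 12 and some subjects may not complete. The absence of any repeat-dose Cmax applies to Cohort 2 on the weekly option only; Cohort 1 keeps its Day 28 profile.

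The impact is low to moderate: the endpoint is secondary, there is no hypothesis test, and the data are still reported as concentrations. It should still be corrected, because a named secondary endpoint has a derivation rule that does not match its sampling schedule, and settling the days before database lock avoids choosing them once the data are known.

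**What to change.** Make the parameter table in SAP 4.8.1 specific to cohort and schedule:

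- **Cohort 1:** all listed parameters on Days 0 and 28, unchanged.
- **Cohort 2, every-other-week maintenance:** Cmax and Tmax only, on Days 0, 7, 14, 28 and 84.
- **Cohort 2, weekly option:** Cmax and Tmax only, on Days 0, 7, 14, 21 and 84.
- Label the terminal rate constant, half-life and both AUCs as Cohort 1 only, so that the table agrees with SAP 3.2.11.

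This brings coverage in Cohort 2 to 5 of 5 PK days, or up to 60 subject-occasions with 12 subjects. The cost is SAP wording and the matching table shells. No visit or sample is added, because every day listed is already in the schedule of assessments.

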4.8.2 Pharmacodynamic / Disease Activity Analysis

PD samples will be collected for analyses throughout the study. PD samples will be collected according to the schedule shown in [Table 5](#).

Measurements for PD and disease activity biomarkers include:

- Total IgG assessments
- IgG subtypes (IgG1-4)
- Immunoglobulin A (IgA)
- Immunoglobulin M (IgM)
- Albumin levels
- CIC
- Hematocrit
- Hemoglobin
- Platelet count
- Reticulocyte count
- LDH
- Haptoglobin
- Direct Coombs tests
- Total and indirect bilirubin

PD/disease activity values, percentage change and absolute change from baseline will be summarized by cohort using descriptive statistics if result type is numerical. Mean (\pm SD) of values and percentage change and absolute change from baseline will be plotted by cohort. PD/disease activity result categories will be summarized if result type is categorical.

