### 5.3 Exclusion Criteria

A subject who meets any of the following criteria is ineligible for the study:

1. Subject unable or unwilling to comply with the protocol.
2. Active non-hematologic malignancy or history of non-hematologic malignancy in the 3 years prior to screening (exclusive of non-melanoma skin cancer and cervical cancer in situ).
3. Karnofsky Performance Scale  $\leq 50$ .
4. Estimated glomerular filtration rate (eGFR)  $< 45$  mL/minute/1.73m^2.
5. Platelet count  $< 30 \times 10^9$ /L.
6. Corrected reticulocyte count  $< 2\%$  (using the following calculation; (% reticulocyte x % hematocrit) / normal hematocrit [45%]).
7. Positive for human immunodeficiency virus (HIV) or hepatitis C antibody.
8. Positive for hepatitis B surface antigen.
9. Splenectomy within 3 months of screening.
10. Any T-cell or NK-cell NHL, and any moderate- or high-grade B-cell lymphoma, including Burkitt lymphoma, lymphoblastic B-cell lymphoma, diffuse large B-cell lymphoma, mantle cell lymphoma, or small non-cleaved cell non-Burkitt lymphoma.
11. Received any cytotoxic (other than azathioprine, chlorambucil, low-dose methotrexate, or low-dose oral cyclophosphamide [ $\leq 100$  mg/day]), or any non-anti-CD20 mAb therapy in the 3 months prior to screening.
12. Any exposure to an investigational drug or device within 30 days prior to screening.
13. IVIG treatment within 30 days of screening.
14. Plasmapheresis or immunoadsorption within 30 days of screening.
15. Cellular therapy, including chimeric antigen receptor and T-cell (CAR-T), at any time prior to screening.
16. Use of any immunosuppressive drugs within 3 months of screening, not including those allowed by the inclusion criteria.
17. Active infection or history of recurrent infections.
18. Serum total IgG  $< 600$  mg/dL.
19. Subject has any current medical condition that, in the opinion of the Investigator, may compromise their safety or compliance, preclude successful conduct of the study, or interfere with interpretation of the results (eg, a significant pre-existing illness or other major comorbidity that the Investigator considers may confound the interpretation of the study results).
20. Any vaccination within 2 weeks of screening.

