### **Prohibited Medications**

The following treatments are prohibited during the study unless specified above as permitted:

1. Rituximab or other anti-CD20 antibody
2. Monoclonal antibodies other than study drug.
3. Any immunosuppressive drugs apart from those that are listed as permitted.
4. Any cytotoxic agent other than azathioprine, chlorambucil, low-dose methotrexate, or low-dose oral cyclophosphamide ( $\leq 100$  mg/day).
5. IV corticosteroids prior to infusion of study drug (except in subjects who received corticosteroids for treatment of a prior infusion reaction to SYNT001).
6. Any investigational drug or device.
7. Vaccinations within 2 weeks of screening through 28 days following final dose of study drug.

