### 9.6.3 Potential Immune Effects

An antibody blocking FcRn is anticipated to have several effects. These include acceleration of catabolism of IgG, but not other immunoglobulin isotypes such as IgA and IgM, leading to dose-dependent decreases in circulating IgG levels by up to an estimated 50% from the baseline levels

after a single dose and further decreases after multiple doses up to a 70% to 80% reduction. Based on studies in humans, it is expected that with a single dose, the nadir of this effect will occur approximately 5 days after dosing. The time course of recovery of IgG following dosing in the Phase 1a study suggests that a return to within 30% of baseline levels observed at pretreatment occurs within 4 weeks after a single dose and within 4 weeks after multiple doses as shown in NHPs.

Given the normal adult range of total IgG of 500 to 1600 mg/dL ([Agarwal and Cunningham-Rundles, 2007](#); [Furst, 2009](#); [Gonzalez-Quintela et al., 2008](#); [Jolliff et al., 1982](#); [Keystone et al., 2007](#); [McMillan et al., 1997](#); [van Vollenhoven et al., 2013](#)), with a mean of 1150 mg/dL, a 50% decrease in mean total IgG would translate to 575 mg/dL and a 50% decrease from the low end of the normal range used for the inclusion criteria of 600 mg/dL in this study would be to 300 mg/dL. An 80% decrease from baseline after multiple doses would result in IgG levels of 230 mg/dL and 120 mg/dL, respectively. While these levels are in the range found in patients with primary humoral immunodeficiency ([Ameratunga et al., 2013](#)), the levels will be transient. Further, in other conditions, the temporary (ie, less than 4 months) depletion of IgG (up to 95% reduction of total IgG as seen with immunoadsorption) does not appear to impart an increased risk of infection ([Eming and Hertl, 2006](#); [Furst, 2009](#); [Keystone et al., 2007](#); [Schmaldienst et al., 2001](#); [van Vollenhoven et al., 2013](#)). Study subjects will be monitored clinically for any infection. Further, commercial IVIG can be given to immediately restore IgG levels in case of a bacterial infection occurring while their IgG levels are decreased.

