4. STATISTICAL METHODOLOGY

All descriptive and inferential statistical analyses will be performed using Statistical Analysis System (SAS®) software Version 9.3 or higher.

Phoenix WinNonlin Version 6.4 or higher will be used in the determination of the PK terminal phase and the calculation of PK parameters. PK parameters will be calculated via SAS and verified with the Phoenix WinNonlin results.

Missing data will not be imputed unless otherwise stated. All clinical data captured will be provided in data listings.

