4.4 Demographics and Baseline Characteristics

Demographics and baseline characteristics will be summarized descriptively by cohort and in total for the Safety population and repeated for PK and PD populations if they are different from the Safety population.

Demographic and baseline characteristics include, but are not limited to, age at informed consent, gender, race, ethnicity, body weight, and body mass index (BMI), age at diagnosis of WAIHA, WAIHA disease duration, and Karnofsky Performance Scale score (%).

Continuous variables (e.g., age, weight, and BMI) will be summarized by descriptive statistics. Categorical variables (e.g., gender, race, and ethnicity) will be summarized by the number and percentage of subjects in corresponding categories.

Baseline is defined as the Day 0 (pre-dose) measurement. If missing, the last measurement prior to the first study drug administration will be used as the baseline value.

Medical/surgical history will be coded using the Medical Dictionary for Regulatory Activities (MedDRA 19.1) and summarized for the number and percentage for each System Organ Class (SOC) and preferred term by cohort and in total for the Safety Population. Hematologic variables history will also be summarized. All medical/surgical history and hematologic variables history will also be listed.

A summary table for categories of protocol deviations will be produced for major protocol deviations. Protocol deviations will also be listed for the Safety population.

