4.9.2 Blood Transfusions

The number of units of packed red blood cells received by subjects will be summarized by cohort.

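### SAP 4.8.2 pools hemoglobin, hematocrit and IgG values taken after transfusion or IVIG into the cohort means and mean plots; one supportive display without them would help (minor)

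*SAP*

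**What the plan says.** SAP 4.8.2 covers hemoglobin, hematocrit, total IgG and IgG subclasses in one rule: "PD/disease activity values, percentage change and absolute change from baseline will be summarized by cohort using descriptive statistics". Means with SD, for values and for changes, are then plotted by cohort. The related objective in SAP 2.1.2 is worded as efficacy: "To assess the efficacy of doses of SYNT001 at different dose levels and dosing regimens on disease markers".

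The general rules do not deal with an intervening treatment. SAP 4 says that "Missing data will not be imputed unless otherwise stated", and SAP 4.4 that "Baseline is defined as the Day 0 (pre-dose) measurement", with the last pre-dose value as fallback. The laboratory summaries in SAP 4.7.2 set no condition either. Protocol 11.3 defers missing-data methods to the SAP, and Protocol 11.6 repeats the descriptive plan.

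Both treatments are foreseen. Transfusion has an exploratory objective (Protocol 3), analyzed in SAP 4.9.2: "The number of units of packed red blood cells received by subjects will be summarized by cohort". For IVIG, Protocol 9.6.3 says that "commercial IVIG can be given to immediately restore IgG levels in case of a bacterial infection" while IgG is lowered. The list in Protocol 6.10 that opens "The following treatments are prohibited during the study unless specified above as permitted" names neither. Before entry, Protocol 5.3 excludes "IVIG treatment within 30 days of screening"; it has no matching criterion for transfusion.

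**The concern.** Subjects enter with hemoglobin below 11 g/dL and active hemolysis. If a subject worsens and is transfused, the next value can rise, and under the all-values rule that rise counts in the cohort mean like any other. A transfusion shortly before Day 0 works the other way: it lifts the baseline and shrinks the later change. IVIG given on study adds IgG and so hides part of the reduction that the drug is meant to produce.

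With no control arm, nothing in the design averages these effects out, and with at most 8 or 12 subjects per cohort one person carries visible weight. At stake is the reading of two displays, the mean change in hemoglobin or hematocrit and the mean change in IgG, under an objective that speaks of efficacy. Red-cell units are totalled by cohort and are not tied to visits, so no planned output links a transfusion to the hemoglobin value that follows it.

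**Working it through.** The plan gives no figure to reproduce: no sample-size calculation was made, and neither the frequency of transfusion or IVIG nor their effect is stated. What follows is illustration.

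**Inputs**
- Cohort sizes: n = 8 and n = 12, the maxima in SAP 3.1.
- Hemoglobin rise due to transfusion at the visit: 0.5 to 3 g/dL. This is an assumption; the documents give no value.
- IgG reduction: 59%, the observed mean in patients (Protocol 2.2). Also 50% to 68%, modelled during maintenance for one Cohort 2 regimen (same section).
- Share of the IgG fall that IVIG reverses in the affected subject: half or all. This is an assumption.

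**Transfusion after Day 0, one subject.** Shift in mean = rise / n.
- n = 8: 0.5/8 = 0.06 and 3/8 = 0.38 g/dL.
- n = 12: 0.5/12 = 0.04 and 3/12 = 0.25 g/dL.

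**Transfusion before Day 0, one subject.** If a share f of the rise persists at the later visit, shift in mean change = −(1 − f) × rise / n. At n = 8:
- f = 0: −0.06 to −0.38 g/dL.
- f = 0.5: −0.03 to −0.19 g/dL.
- f = 1: 0.

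**IVIG, one subject, everyone otherwise at reduction R.** Full return: R × (n − 1)/n. Half return: R × (n − 0.5)/n.
- n = 8, R = 59%: 59 × 7/8 = 51.6% (full); 59 × 7.5/8 = 55.3% (half).
- n = 12, R = 59%: 59 × 11/12 = 54.1% (full); 59 × 11.5/12 = 56.5% (half).
- n = 12, R = 50% and 68%: 45.8% and 62.3% (full).

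**Median in the same example.** At n = 8, seven subjects have a 59% reduction and one has 0%. The mean reads 51.6%, the median still reads 59%, and the range exposes the outlier.

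**Visits lost to a 14-day window.** For a transfusion on day d, from Day 0 to the last dose day, count nominal hemoglobin visits v with d < v ≤ d + 14.
- Cohort 1 (Days 0, 7, 14, 21, 28, 33, 42, 56, 84, 112): 2 to 3 of 10.
- Cohort 2, every other week (Days 0, 7, 14, 28, 42, 56, 70, 84, 91, 140): 1 to 2 of 10.
- Cohort 2, weekly (Days 0 to 84 by 7, then 91 and 140): 1 to 2 of 15.

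**The case against.** The best reply is that the plan already carries resistant statistics. SAP 4.1 requires the median, quartiles, minimum and maximum for continuous data, and in the example above the median does not move. An all-values summary is also a legitimate choice. SAP 1 allows supplementary analyses to be added and identified in the study report. The size rests on an assumed rise and an unknown number of affected subjects, and its low end is negligible. On-study IVIG rests on one contingency sentence, and its effect would understate the drug's action on IgG. A reader can trace much by hand from the listings, the concomitant-medication tables (SAP 4.5) and steroid use by visit (SAP 4.9.3).

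Most of this stands, and it lowers the priority. Three things remain. The plots in SAP 4.8.2 show means only. Listings let a reader explain a mean but leave it unchanged. The permission in SAP 1 does not pre-specify which values would be set aside, so the choice would be made with the data in view.

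Two stronger readings are tempting. A reader might infer that the choice of the Cohort 2 regimen would be distorted, because PD data inform it. The documents do not support that: Protocol 11.8 and SAP 7 say no statistical analyses are planned to aid dose-escalation decisions, so no planned decision uses these tables.

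A reader might also infer that values after any change in WAIHA therapy, a steroid taper or infusion-related steroids need the same exclusion. Protocol 6.10 asks for stable WAIHA treatment until 14 days after the last dose, and SAP 4.9.3 already summarizes steroid use and dose by visit. Such an exclusion would have no natural end. A Cohort 1 taper starting on Day 42 (28 + 14) would remove Days 56, 84 and 112, which is 3 of 10 hemoglobin visits.

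**Conclusion.** The gap is real but minor. As written, SAP 4.8.2 mixes post-transfusion hemoglobin and hematocrit, and post-IVIG IgG, with drug effect in the cohort means and mean (SD) plots. With one affected subject and the assumed rise, the hemoglobin mean shifts by 0.06 to 0.38 g/dL at n = 8 or 0.04 to 0.25 at n = 12. It is overstated if the transfusion follows Day 0, and the change is understated by at most the same amount if it precedes Day 0. A 59% IgG reduction reads 51.6% to 55.3% at n = 8. More affected subjects would enlarge these shifts; the documents do not say how many to expect.

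The exposure lies mainly in the means and their plots, since the planned medians, quartiles and ranges largely withstand one affected subject. The endpoints are secondary and descriptive, so no test or error rate is touched. The conclusion is limited to the SAP text: SAP 6 places the table shells and derived-data specifications in separate documents that were not available and could hold a rule, although SAP 4.8.2 does not point to one.

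**What to change.** Before database lock, keep the all-values summaries and plots in SAP 4.8.2 as the main version. Add one supportive summary and plot, with n shown at each visit, that leaves out:

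1. hemoglobin and hematocrit within a pre-specified window after a red-cell transfusion (for example 14 days). This includes an affected Day 0 value, in which case the subject leaves the change-from-baseline rows of this version;
2. total IgG and IgG subclasses within a pre-specified, finite window after on-study IVIG.

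Mark transfusion and IVIG dates beside the individual hemoglobin and IgG values. Do not extend the exclusion to changed WAIHA therapy, tapers or infusion-related steroids.

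First confirm that transfusion dates are captured. Protocol 6.10 records start date and time for medications, but no section says so for transfusions. For early enrollees, SAP 3.2.19 notes that before amendment 5 medications were documented from 14 days before enrollment, with primary-disease treatment history collected further back.

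The cost is a short SAP addition, some programming and one supportive set of displays. The windows are conventions, each transfusion removes 1 to 3 hemoglobin visits for that subject at 14 days, and the exclusion may be selective. The added version is therefore supportive only and does not by itself isolate the drug effect.
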